7.4 Enrollment Visit: CRF

The study physicians will identify eligible patients at regularly scheduled office visits. Upon determining that the patient has at least 6 month history of GERD and has been identified as a first time partial responder to optimized PPI treatment, the study physician and/or designated staff will attempt to recruit the patient for the study. If a patient indicates that he or she is interested in participating, the physician will advise the patient of the nature of the study, study requirements, and study benefits using a study recruitment packet. The recruitment packet will include a study description, copy of the informed consent form, and a copy of the baseline patient survey.

The physician will ensure that the subject is given full and adequate oral and written information about the nature, purpose, possible risk and benefit of the study and will ensure that the subjects are notified that they are free to discontinue from the study at any time. This will also ensure that the subject is given the opportunity to ask questions and allowed time to consider the information provided.

The study physician will obtain informed consent from the patient and have the patient sign two copies of the informed consent form (ICF), one set of copies will be given to the patient to keep

and one set will be filed with the study materials for that patient. Signed and dated informed consent must be available before any other study procedures are conducted. Each patient will have a unique identifier assigned at the enrollment visit that will be used for all electronic and hard copy documents. Patients will officially be recruited in the study once they sign the informed consent form.

In order to finalize the screening process, the physician will confirm that the patient meets all study criteria as outlined in the CRF. Once this has been confirmed, the patient will, as a second step, complete the RDQ-RI. To be eligible for enrolment, the patients must have reported in the RDQ-RI screening instrument, using 7 days recall, a minimum of 3 days with at least one of the two following symptoms with at least moderate severity:

- a burning feeling behind the breastbone;
- an unpleasant movement of material upwards from the stomach.

The study physicians will also complete the visit 1 of the CRF for each subject to document enrollment into the study.

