All subjects for whom a signed informed consent form and a completed baseline CRF, proving eligibility of the patient, are submitted will be considered enrolled in the study. Baseline CRF pages will also be collected for patients who fail study eligibility. The baseline RDQ-RI won't be collected for patient failing to one or more inclusion criteria from the baseline CRF. However, the baseline RDQ-RI will be collected for all the patients meeting all other baseline entry criteria, whatever there eligibility on this specific instrument (RDQ-RI).

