7.5 Enrollment Visit: Patient Survey

At the time of the enrollment visit, study physicians and/or designated staff will provide to each subject a paper patient survey.

Sites will provide a private place, where subjects are not distracted and can concentrate on the completion of the questionnaires. Subjects will be asked to complete the general Health-related Quality of Life questionnaires first, followed by the disease specific questionnaires. After completion of the survey, subjects will be asked to return the completed documents to site staff in a sealed envelope for mailing back to i3. The package that will be mailed back to i3 will also contain the baseline RDQ-RI.

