7.9 Study Assessments

Data will be collected using a case report form, a patient baseline survey, and four follow-up patient surveys at 3, 6, 9 and 12 months. A summary of each assessment appears in the sections below.

Schedule of Completion	Total Questions	V1	3 months	6 months	9 months	12 months
Physician CRF						
Eligibility and demographics, history, comorbidities	20	X				
Physician CRF / Patient Survey:						
Resource Utilization						
Hospital visits, physician's office visits, prescriptions	~10	X		X		X
Patient Survey:						
Resource Utilization						
Over the counter medication, other physicians			X	X	X	X
Anxiety & Depression						
Hospital Anxiety and Depression Scale (HADS)	14	X				X
Symptom Frequency and Severity						
Reflux Disease Questionnaire (RDQ-RI)	26	X	X	X	X	X
GERDQ	6	X		X		X
Quality of Life						
Quality of Life in Reflux and Dyspepsia (QOLRAD-RI)	25	X		X		X
EQ-5D	6	X		X		X
Short Form 36 (SF-36)	36	X		X		X
Work Productivity						
Work Productivity and Activity Impairment for Patients with Gastroesophageal Reflux Disease (WPAI-GERD)	6	X	X	X	X	X

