7.9.2 Patient Baseline and Follow-Up Surveys

The patient survey will include the following patient reported outcomes questionnaires:

Symptom Frequency and Severity

- The Reflux Disease Questionnaire (RDQ-RI) is a 26-item, self-administered questionnaire designed to assess the frequency and severity of heartburn, acid regurgitation and epigastric pain over the previous week¹⁹. A GERD dimension can be obtained by combining the heartburn and regurgitation dimensions, while the epigastric pain dimension is also known as the dyspepsia dimension.

Symptom frequency and severity are scored on a 6-point Likert scale, with higher scores indicating more frequent or severe symptoms.

- The GERDQ is a 6-item questionnaire that measures symptoms in the upper gastrointestinal tract.

Quality of Life

- The Quality of Life in Reflux and Dyspepsia – Reflux Inhibition (QOLRAD-RI) questionnaire is a disease-specific quality of life instrument comprising 25 items that ask subjects about the effect of upper gastrointestinal symptoms on five dimensions: emotional well-being, sleep, vitality, eating/drinking and physical/social functioning²⁰. Subjects report the frequency of these effects during the previous week using a 7-point Likert scale, ranging from one (all of the time/a great deal) to seven (none of the time/none at all), with low scores indicating a severe impairment of daily functioning.
- The SF-36 is a 36-item general quality of life instrument that measures physical functioning, bodily pain, and role limitations due to physical health problems, role limitations due to personal or emotional problems, emotional well-being, social functioning, energy/fatigue, general health problems, and perceived change in health. It yields an eight-scale profile of functional health and well-being scores as physical and mental health summary measures and a preference-based health utility index.²¹ Item response categories range from dichotomous to six levels and are scored so that a higher score indicates a more favorable health state.
- The EQ-5D is a health-outcome measure that provides a descriptive profile and index value for health status.²² Five questions comprise dimensions of health (mobility, self-care, usual activities, pain/discomfort, anxiety/depression) across three levels (no problems, some/moderate problems, and extreme problems), in addition to one measure of health status on a vertical graduated (0-100) visual analog scale.

Anxiety and Depression

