10.2 Study Population

Two study populations are considered: the “log population”, which consists of all GERD patients approached for this study and the “per protocol population”, which consists of all patients enrolled in the study, satisfying to inclusion and exclusion criteria specified in section 5.

The proportion of partial-responders to PPI and analysis of screening failure will be conducted over the log population and the analyses of symptoms, patients reported outcomes, healthcare

resource use, productivity loss and associated costs will be performed on the per protocol population.

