10.3 Descriptive Analysis

First, frequency tables reporting the characteristics of the log population, proportion of partial-responders to PPI and reason for exclusion will be prepared.

A descriptive analysis will first be undertaken. For continuous endpoints the following will be reported:

- mean
- median
- standard deviation
- 95% confidence intervals for the mean
- minimum
- maximum
- first and third quartiles.

The distribution plot of the variables will also be presented. For categorical variables, we will report frequency tables and histograms.

The following analysis will be reported by physician type (General practitioner, gastroenterologist) and overall.

- Descriptive statistics will be provided for patients' characteristics (age, gender, height, weight, BMI, smoking status).
- Medical history at study entry will be described using retrospective data collected from the physician. This will include the frequency of co-morbidities in partial responders to PPI (proportion of patients having each type of co-morbidities), time since diagnosis of GERD and treatment history of GERD. The treatment history will be described via the proportion of patients having used each type of healthcare resource use and the mean level of resource use by type (diagnostic test by type, surgery, referral to a specialist, prescribed medication by type, dose and frequency).
- The medical treatment pathways will be further described by reporting the proportion of patients receiving each medication as first, second and third treatment and by reporting the frequency of each possible strategy (defined via the sequence of medications prescribed to the patient).

-
- Symptom frequency and severity scores (based on RDQ-RI and GERDQ) will be reported by visit. Graphs providing the mean score value and 95% confidence interval over time (at visit 1, then 3, 6, 9, 12 months) will be prepared.
 - For each quality of life and patient reported outcomes questionnaires (SF-36, QOLRAD - RI, EQ-5D), item, domain and total scores will be estimated according to the scoring instructions from each questionnaire. Each type of score (item, domain and total) will be reported by visit using tables and graphs indicating the mean value and 95% confidence interval over time.

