10.6 Multiple regression

To investigate the link between symptom (frequency and severity) and QOL we propose to conduct a number of analyses consisting of correlation analysis, graphical analysis and generalised linear modeling. GLM are selected to account for underlying distribution of endpoint of interest (non-normal). We would model QOL score as a function of patients' characteristics, symptoms, adverse effects and medical history, to quantify the impact of each factor on the QOL impairment. Similar types of analyses would be performed for resource use, productivity losses and costs.

In addition we will develop longitudinal models to understand the evolution of the study endpoints over time to quantify the consequences of reducing the symptom frequency and/or severity in terms of costs, quality of life and utility values. We would use generalized estimating equation modeling to model the study endpoint dynamically and account for the between-patient heterogeneity. Generalised Estimating Equation models would be used here to estimate the heterogeneity between-patients vs within patient and to understand the impact of change in symptoms (reduction of frequency, severity) on study endpoints. These analyses would be performed for HRQOL, utility values, productivity loss, healthcare resource use.

Bivariate analyses will be conducted to assess whether each factor of interest (patients' characteristics and symptoms frequency and severity) significantly affects quality of life, resource use, productivity loss and associated costs. The heterogeneity between sites and between patients will be reported via the analysis of intraclass coefficients.

The results of these preliminary analyses will be used to develop generalized linear mixed model, accounting for the underlying distribution of the modeled endpoints and the clustering of the data (patient's repeated measures nested within sites).

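### The RDQ-RI form that decides eligibility is also the only V1 value, so the V1 mean and any fitted trend starting at V1 include regression to the mean

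*Protocol*

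**What the plan says.** **Selection.** Section 7.4 states: "To be eligible for enrolment, the patients must have reported in the RDQ-RI screening instrument, using 7 days recall, a minimum of 3 days", for at least one of two symptoms (heartburn or regurgitation) at moderate severity or worse. This is inclusion criterion 5 in section 5.

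**The same form is the baseline.** Section 7.4 calls it the baseline form and keeps it even when the patient fails on it: "the baseline RDQ-RI will be collected for all the patients meeting all other baseline entry criteria". Section 7.5 sends it in with the enrolment survey: "The package that will be mailed back to i3 will also contain the baseline RDQ-RI". The schedule in section 7.9 shows one RDQ-RI at V1 and one each at months 3, 6, 9 and 12. It has no screening column, run-in or repeat baseline. Section 7.9.2 gives the recall window: the questionnaire is "designed to assess the frequency and severity of heartburn, acid regurgitation and epigastric pain over the previous week".

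**Analysis.** Section 10.2 restricts the symptom analyses to "all patients enrolled in the study, satisfying to inclusion and exclusion criteria specified in section 5". Section 10.3 then specifies: "Graphs providing the mean score value and 95% confidence interval over time (at visit 1, then 3, 6, 9, 12 months) will be prepared". Section 10.6 adds longitudinal models of how the endpoints evolve, which also serve "to understand the impact of change in symptoms (reduction of frequency, severity) on study endpoints".

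**The concern.** V1 is cut off from below by the entry rule, while months 3 to 12 are not. A patient whose symptoms vary from week to week is more likely to enter after a bad week, and the later weeks will on average be milder. The mean curve should therefore step down after V1 without any real change.

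Symptom load, impact on daily life and work productivity are primary objectives (section 3.1). QOLRAD-RI and WPAI-GERD cover the same past week as the screening form, so their V1 values, and the productivity cost at study entry in section 10.5, may carry part of the shift. Any real change in care after a patient is identified as a partial responder falls in the same V1-to-month-3 interval. With no comparator, the curve cannot separate the two. The protocol itself fixes the entry rule, the single form, the population and V1 as the first plotted point, so this is more than detail left to the SAP.

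**Working it through.** The protocol states no figure for regression to the mean, so there is none to reproduce.

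**Inputs from the protocol.** The entry rule (sections 5 and 7.4), a single V1 form (7.4, 7.5, 7.9), a one-week recall (7.9.2), and about 200 patients for analysis (section 6).

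**Assumed inputs.** The share p of patients completing the RDQ-RI who pass it, and the correlation rho between the scores of two separate weeks. The protocol gives neither, so ranges are shown.

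**Expected fall with no true change.** Treat the score as standard normal before screening, with the top share p admitted (cut-off c).

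- Mean at V1 among those admitted: lambda(p) = phi(c)/p
- Mean at a later week: rho × lambda(p)
- Fall: (1 − rho) × lambda(p), in SDs of the pre-screening score

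For example, at p = 70%, lambda = 0.497. The fall is 0.5 × 0.497 = 0.25 SD at rho 0.5 and 0.2 × 0.497 = 0.10 SD at rho 0.8.

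| Pass rate | rho 0.5 | rho 0.7 | rho 0.8 |
|---|---|---|---|
| 50% | 0.40 | 0.24 | 0.16 |
| 70% | 0.25 | 0.15 | 0.10 |
| 80% | 0.17 | 0.10 | 0.07 |
| 90% | 0.10 | 0.06 | 0.04 |

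At p = 95% and rho 0.5 the fall is 0.05 SD.

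**Scale.** The 95% half-width of a single mean at n = 200 is 1.96/√200 = 0.14 SD, before allowing for truncation. Measured as a paired within-patient change at n = 200, the 70% case lies 3.8 (rho 0.5) to 2.3 (rho 0.8) standard errors from zero, and the 90% case 1.4 to 0.9.

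**The rule itself, simulated.** Patients have stable daily symptom rates, and entry requires 3 or more of 7 days.

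| Eligible | Mean symptom days, entry week | Later week | Below entry threshold in the later week |
|---|---|---|---|
| 67% | 4.62 | 4.21 | 18% |
| 80% | 4.88 | 4.60 | 12% |
| 95% | 5.44 | 5.34 | 4% |

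**Effect on the section 10.6 models, simulated** at p = 70% and rho = 0.7, with a true slope of QoL on symptoms of −1. The week-to-week variance is either all real fluctuation, half real and half error, or all error.

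- Mean symptom change from selection alone: −0.15 SD in each case.
- Mean QoL change: +0.15, +0.07 and 0.00. QoL shares the shift only as far as the fluctuation is real.
- Slope of QoL change on symptom change, without and with selection: −1.00 and −1.00; −0.50 and −0.50; 0.00 and 0.00.
- Pooled slope of QoL level on symptom level, without and with selection: −1.00 and −1.00; −0.85 and −0.82; −0.70 and −0.64.

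Selection shifts the means, and with them any time trend. It leaves the change-on-change slope alone. The weakening of that slope comes from measurement error and is present without selection.

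**The case against.** **The effect may be small.** The RDQ-RI is completed only after the physician has identified a partial responder on optimized PPI and confirmed the other criteria. A pass rate of 90% or more is plausible, and the fall is then at most 0.10 SD over the correlations shown. The formula also treats the plotted score as the screened variable, whereas the rule counts days on either of two symptoms and does not screen on epigastric pain at all. If a score correlates 0.7 with the screening variable (assumed), the 70% figures shrink to 0.7 × 0.25 = 0.17 and 0.7 × 0.10 = 0.07 SD. This stands: the size is uncertain and could be negligible.

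**The plotted intervals may not show it.** A reader might infer from the 2.3 to 3.8 standard errors that the graph will display a clear improvement. Those figures are for a paired change, while section 10.3 plots a separate interval at each visit. At 70% pass and rho 0.8, the fall of 0.10 SD is smaller than the month-3 half-width of 0.114 SD. This stands too.

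**The protocol claims no improvement.** The study is descriptive, without hypotheses, and V1 validly describes symptom load at the time of identification. That is correct. The risk lies in how the step from V1 is read, and in a fitted trend that includes it.

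**Much of this is SAP detail.** Graph labels and model terms often are. The single form for selection and baseline, and the curve that starts from it, are nevertheless set in the protocol.

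**Conclusion.** The point holds in limited form. One form both selects patients and supplies V1, so the V1 RDQ-RI mean, and any V1-to-follow-up trend in section 10.6, includes regression to the mean. V1 scores of QOLRAD-RI and WPAI-GERD may share part of it. With no true change, the expected fall is about 0.16–0.40 SD at 50% pass, 0.10–0.25 at 70%, 0.07–0.17 at 80% and 0.04–0.10 at 90%. These figures assume rho between 0.8 and 0.5 and a normal score that is itself the screening variable; they are smaller for scores only partly correlated with the rule.

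A reader might go further and infer that the symptom-change models will turn this artefact into apparent cost or utility gains. The documents do not support that: under the check above, selection on V1 does not bias the slope of endpoint change on symptom change. Nor can one say that a misleading fall will certainly be visible, since neither the pass rate nor the correlation is known. It is a cheap improvement worth making.

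**What to change.** **Section 10.3.** Keep V1 on the RDQ-RI graph but mark it as the selection week. Describe the trend from months 3–12, and state that the V1-to-month-3 fall is not to be read as improvement. Report the RDQ-RI pass rate and the score distribution of all screened patients, including those who failed only on this form. Section 7.4 already collects these forms, and they show how strong the truncation is. They do not give a full correction, because the protocol describes no follow-up of patients who fail.

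**Section 10.6.** In models of evolution over time, fit visit as a factor or give V1 its own indicator, so that the V1 step does not drive the trend. Keep V1 in the QoL and utility models: QOLRAD-RI, EQ-5D and SF-36 are taken only at V1, 6 and 12 months, and dropping V1 would leave a single change interval.

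**Cost.** A label, a table and one model term, all on data already planned. The small downside is that the V1-to-month-3 change carries less weight in the described symptom course.

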10.4 Calculation of Direct Costs: Medical Resource Utilization

Using physician-reported resource utilization data and OTC medications collected from the patients, unit cost for individual services will be derived for the purpose of estimating costs. Following database lock, a unique list of the health care resources reported will be obtained and unit costs for each resource will be identified from standard costing sources. Standard cost sources will include national administrative databases (e.g., hospitalization, ER visit) and patient surveys for outpatient procedures. Unit costs of medications will be obtained from the Vidal. These unit costs will be applied to the resource utilization reported by the patients and used to calculate overall costs of healthcare. Costs will be computed from the third party payer perspective.

The mean cost of healthcare will be reported by visit (at study entry, 6 months and 12 months) and type of healthcare resource use.

The mean cost of healthcare resource use will also be reported by physician type (GP vs specialist), patients' characteristics (age class, gender, BMI class) and frequency and severity of symptoms. The summary statistics will be reported over time and by group in the form of tables and graphs.

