1 PROTOCOL SYNOPSIS

Title	Partial Responders to PPI treatment: the Cost to Society and the Burden to the Patient – a study in France (REMAIN Study –French Arm)
Protocol Number	Study code D9120N00013
Study design	French arm of a multi-center, prospective, observational, non interventional study
Patients	Patients with Gastroesophageal Reflux Disease (GERD) newly classified as partial-responders to proton pump inhibitors (PPIs)
Period for Patient Participation	
Primary objectives	
– To describe common treatment pathways, including extent of and time to referral to specialists;– To collect resource utilization data;– To collect relevant cost estimates and calculate cost per patient;– To assess the symptom load, impact of symptoms on daily life and effect on work productivity.
Secondary objectives	
– To estimate the proportion of new partial-responders to all new patients with GERD
Inclusion criteria	
1. Provision of signed informed consent.2. Able to read and write in French and able to comply with study requirements.3. Female or male, aged 18 years or above.4. The patient must at the enrolment visit be identified for the first time as partial responder to PPI treatment as defined by the following criteria:
a) At least 6 month history of GERD symptoms (need not be consecutive)b) Continuously treated with unchanged optimized PPI treatment for any GERD indication during the last 4 weeks (an optimized PPI treatment is a treatment, which according to the investigators judgment cannot be further improved by changing brand or dosing of the PPI) .c) Patients with a history of reflux (erosive) esophagitis Los Angeles grade A-D must have been continuously treated with a PPI during the last 8 weeks before enrolment (optimized PPI treatment during the last 4 weeks before enrolment).

	
5. To be eligible for enrolment, the patients must have reported, in the RDQ-RI screening instrument using 7 days recall, a minimum of three days with at least one of the two following symptoms with at least moderate severity:
 
 • a burning feeling behind the breastbone • an unpleasant movement of material upwards from the stomach.

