3 STUDY OBJECTIVES

3.1 Primary Objectives

The primary objectives of this observational, prospective study are

- to describe common treatment pathways, including extent of and time to referral to specialists
- to collect resource utilization data
- to collect relevant cost estimates and to calculate the cost per patient
- to assess the symptom load, impact of symptoms on daily life and effect on work productivity
- to assess the effect of partial response on HRQoL

in patients with GERD newly identified as partial responders to PPI treatment.

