7.6 CRF: Resource utilization

The study physician will complete a hard copy CRF documenting the patient's medical resource utilization related to GERD such as office visits, prescriptions, hospitalizations etc at month 6 and 12 following study entry. Data regarding over the counter medication and visit to other

physicians will be collected from the patient directly via the patient survey document at month 3, 6, 9 and 12 from study entry.

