10.5 Calculation of Indirect Costs: Productivity

Days of work missed due to GERD and obtained from the WPAI-GERD will be converted into monetary amounts utilizing earnings data from the national statistics (INSEE).

The mean cost of productivity loss will be reported by visit (at study entry, 6 months and 12 months) and type of productivity loss (absenteeism, presenteeism, overall).

The mean cost of productivity loss will also be reported by physician type (GP vs specialist), patients' characteristics (age class, gender, BMI class) and frequency and severity of symptoms.

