10.7 Cost of Illness Analysis

The first step of this analysis will consist of estimating the size of the target population. A literature review will be undertaken to obtain the incidence and prevalence of GERD in France and the proportion of patients treated in primary care and secondary care. The proportion of

patients with GERD with incomplete response to PPI will be calculated from the sites' log. The proportion of partial responders will be reported by site, physician type and overall, together with 95% confidence intervals. The size of the target population (partial responders to PPI) in France will then be derived.

Based on the information obtained from the cost of healthcare resources collected alongside this study, we will be able to estimate the cost of partial response to PPI within the year of partial response diagnosis. Some assumptions will be made on the basis of the literature and clinical experts' opinion to estimate the mean cost of treatment over subsequent years. The cost of partial response to PPI will be reported overall and by type of resource (GP visits, specialist visits, diagnostic tests, hospitalization, prescribed medications and OTC medications) for France.

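### The national cost of illness in 10.7 fits neither the payer perspective named in 10.4 nor the cost to society in the title: OTC drugs are in it and lost productivity is not

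*Protocol*

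**What the plan says.** The study title in the synopsis reads "Partial Responders to PPI treatment: the Cost to Society and the Burden to the Patient". Among the primary objectives, section 3.1 lists "to collect relevant cost estimates and to calculate the cost per patient"; it names no perspective.

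Section 10.4, on direct costs, starts from this base: "Using physician-reported resource utilization data and OTC medications collected from the patients". It ends the same paragraph with "Costs will be computed from the third party payer perspective". The OTC data come from the patient, not from the physician's record of prescriptions: section 7.6 assigns "Data regarding over the counter medication and visit to other" physicians to the patient survey at months 3, 6, 9 and 12.

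Section 10.5, on indirect costs, values missed work with national earnings data. It states "The mean cost of productivity loss will be reported by visit", and also by type of loss and by subgroup. It names no perspective.

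Section 10.7 estimates the cost of partial response in France from the healthcare resource costs gathered in the study. It reports a total and a breakdown by resource type. The breakdown has six lines, and the list ends with "prescribed medications and OTC medications) for France". None of the six is productivity.

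**The concern.** The perspective of a cost analysis decides which items count and which price each item carries. A payer total holds what the payer reimburses. A societal total holds all resource costs, whoever bears them, together with lost production. The protocol names the first, has the second in its title, and in 10.7 specifies a total that is neither.

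Cost per patient is a primary objective, and section 10.4 fixes the perspective under which its direct part is computed. Section 10.7 then carries those costs to the national level. A reader who meets one overall figure for France will take it either as a payer budget or as the burden on society, and both readings would be wrong. There is also a point of timing. Section 10.4 has unit costs identified only after database lock, so an unsettled perspective leaves the choice of prices open until the resource data are known.

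**Working it through.** The protocol states no cost figure, so there is nothing to reproduce. The check compares components.

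**Notation, per patient**
- R = payer's share of direct costs other than OTC drugs
- S = patient's share of those same costs
- O = OTC spending at the price paid
- r = share of O that is reimbursed (0 to 1)
- P = productivity cost from 10.5

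**Totals that belong to each perspective**
- Payer = R + rO
- Societal = R + S + O + P

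**Total that 10.7 specifies**

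The breakdown has general-practitioner visits, specialist visits, tests, hospital stays, prescribed drugs and OTC drugs. Section 10.4 gives one source for the unit costs of all medications and makes no separate rule for OTC drugs, so O enters as a full line. For the other lines, 10.4 does not say whether unit costs are full prices or the reimbursed share. Two cases follow.

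| Case | 10.7 total | Minus payer total | Societal total minus 10.7 total |
|---|---|---|---|
| Payer rule applied to non-OTC items | R + O | (1 − r)O | S + P |
| Full prices used | R + S + O | S + (1 − r)O | P |

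In both cases the total exceeds the payer cost by at least (1 − r)O and falls short of the societal cost by at least P. It equals a payer total only if every OTC purchase is reimbursed (r = 1) and, under full prices, S is also zero. It equals a societal total only if nobody loses productive time (P = 0) and, under the payer rule, S is also zero.

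**Is there another total elsewhere?**

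Section 10.4 reports direct costs by visit, resource type and subgroup. Section 10.5 reports productivity costs separately, in a similar way. No section adds the two, and no second perspective is named anywhere in the protocol.

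**Can the gaps be sized?**

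No. O, r, S and P all depend on quantities that the protocol does not give.

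**The case against.** The best defence is that the perspective sentence stands under direct costs and that indirect costs have a section of their own. That is right. A reader might infer that valuing lost work in 10.5 contradicts the payer perspective in 10.4. The documents do not support this: keeping direct and indirect costs apart is ordinary, and the sentence can be read as governing 10.4 alone. The conflict that remains is inside 10.4 (payer perspective and OTC drugs) and in the component list of 10.7.

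It can also be said that the parts are separable. Costs are broken down by resource type, and OTC has its own line in 10.7. A reader could subtract it, and could find the productivity cost in 10.5. This stands too, so it would be too strong to call the results uninterpretable. It does not repair the overall figure, which remains unlabelled and fits neither perspective.

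Three further inferences go too far.
- *All OTC spending is mislabelled as a payer cost.* The protocol does not say who pays for OTC drugs. Self-payment is the natural reading because they are collected from patients apart from prescriptions, but it is an inference. Only the unreimbursed part is at issue.
- *The national cost is the study's main result.* No objective lists it; it appears only in 10.7. The missing productivity line affects that section and not the wording of the cost-per-patient objective.
- *The gap can be put in euros.* One lost hour a week over about 50 weeks at an assumed EUR 15 to 30 gives 1 × 50 × 15 = EUR 750 to 1 × 50 × 30 = EUR 1,500 a year. Both the hour and the wage are assumptions, and the result applies only to an employed patient who loses that hour. The protocol gives no employment share and sets no upper age limit, so this is not the gap per patient.

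Finally, it may be said that the statistical analysis plan will settle the matter. The plan is not at hand, and detail may well be left to it. But the protocol already states both the perspective and the component list, and a plan that followed them faithfully would carry the mismatch forward.

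**Conclusion.** The point holds as an inconsistency between 10.4, 10.7 and the title. The overall figure in 10.7 is higher than a payer cost by any unreimbursed OTC spending and lower than a societal cost by the whole productivity loss, plus any patient share that the payer rule removes from the other items. No planned total answers the title's question.

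The upward part rests on the assumption that at least some OTC spending is not reimbursed. The downward part needs only that some productive time is lost. The direction follows from the text; the size cannot be derived from the protocol.

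Enrolment, instruments and data collection are not affected. The matter should be settled before unit costs are assigned, which the protocol places after database lock.

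**What to change.** Name the perspective of each total in 10.4 and 10.7, and report two totals:
- **Payer:** reimbursed direct costs, without OTC spending that is not reimbursed.
- **Societal:** direct costs including any patient share, plus OTC spending, plus the productivity cost from 10.5.

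Add a productivity line to the breakdown in 10.7, and say which of the loss types in 10.5 (absenteeism, presenteeism or overall) enters it. Which perspective is primary is for the sponsor to choose; either resolves the inconsistency once each total is labelled.

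The cost is small but not nil. OTC use and work loss are already collected, so patients are asked nothing new. The change needs one extra costing column and reimbursement rates from outside the study, because the protocol lists no case report form or survey item that records them. It also needs a stated rule for annualising work loss. The WPAI-GERD recalls seven days and is given at entry and at months 3, 6, 9 and 12, so it covers 5 × 7 = 35 days. Section 10.5 reports only entry, month 6 and month 12. The rule should say how all five points yield a yearly figure.
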